8.5. SUBGROUPS

Subgroups will only be assessed for the purposes of exploring the consistency of effects. Data will be summarized for each treatment group and the differences between treatment groups within subject subgroups may be estimated along with 95% confidence intervals

and presented graphically using forest plots. Subgroup analyses are planned for the primary and secondary endpoints.

The following subgroups have been defined:

- Age: <65 years or \geq 65 years
- Sex: male or female
- Race: black/African American, Asian, American Indian/Alaska Native, Native Hawaiian/Pacific Islander, white or other
- Mutational genotype: there will be 2 subgroups, one which identifies the stratification groups (i.e., m.3243A>G or Other) and a second which further splits out the ‘other’ category genotype (i.e., m.3243A>G, m.8344A>G, mt deletion or Other). To split out the ‘other’ genotype category into these extended levels, first the m.8344A>G subjects will be identified from the other description free text field; then mt deletion subjects will be identified as subjects with a single large deletion gene defect; all remaining subjects will be categorized as Other. In the event of a mis-stratification, the actual genotype recorded on the database will be used in analyses.
- Syndromatic phenotype: as identified from the additional symptoms of PMM eCRF page.
 - chronic progressive external ophthalmoplegia (CPEO)
 - Kearns-Sayre syndrome (KSS)
 - Leigh and Leigh-like syndrome
 - maternally inherited deafness and diabetes (MIDD)
 - maternally inherited Leigh syndrome (MILS)
 - mitochondrial encephalomyopathy with lactic acidosis and stroke-like episodes (MELAS)
 - mitochondrial neurogastrointestinal encephalopathy (MNGIE)
 - myoclonic epilepsy with ragged red fibers (MERF)
 - neuropathy; ataxia; and retinitis pigmentosa (NARP)
 - Pearson syndrome (sideroblastic anemia and pancreatic dysfunction)
 - other
- Baseline 12MWD: there will be 2 subgroups \leq 500 m or >500 m and \leq 650 m or >650 m
- Country: all countries that randomized a subject
- Region: North America (USA and Canada), Europe or Australia/New Zealand

- Clinically significant vitamin D deficiency at baseline defined as <30nmol/L: yes, no
- Baseline PROMIS T-score: ≤ 60 or > 60
- Baseline 30STS able to perform test: yes or no
- Long COVID (preferred term of post-acute COVID-19 syndrome) medical history status at baseline: yes, no
- Menopausal status: males, pre-menopausal females or post-menopausal females. Post-menopausal females have a screening FSH value ≥ 23.0 IU/L and with either a date of last menstrual period > 1 year ago from date of first dose or a confirmed clinical history of sterility. Female subjects whose last menstrual period was > 1 year ago but do not have a screening FSH value will also be assumed to be post-menopausal. Female subjects who have a clinical history of sterility but do not have a screening FSH value cannot be classified. This subgroup will only be used for DXA and laboratory bone marker analyses.

The number of subjects in each subgroup has been assessed using blinded baseline data. The review did not identify any subgroup categories to combine, however it has been agreed that only subgroup categories with 5 or more subjects will be summarized and only subgroup categories with 30 or more subjects will be analysed. In addition to this the following decisions were made:

- Race = other will not be summarized
- Country and 30STS subgroups will only be summarized
- All mutational genotype subgroup categories and baseline 12MWD categories will be summarized and analysed
- Syndromatic phenotype subgroup category MERF will be analysed as well as summarized.

9. ANALYSIS OF DISPOSITION, DEMOGRAPHIC AND BASELINE CHARACTERISTICS, AND MEDICATION

9.1. SUBJECT DISPOSITION AND WITHDRAWALS

For the screened set the number of subjects screened, rescreened and randomized and the number who failed screening will be presented. For the randomized set the following number (%) of subjects will be presented:

- Randomized and not treated
- Randomized and dosed
- Completed treatment
- Discontinued from treatment and reason for discontinuation
- Completed study (including subjects who complete the study or those who transition to mavodelpar open-label study at the Week 24 visit). This will be split by those completing at Week 24 (due to transitioning to the mavodelpar open label study) and those completing at follow-up
- Withdrawn from study and reason for withdrawal
- In each analysis set

For each scheduled visit the following number (%) of subjects will be presented for the FAS:

- For on-treatment those who:
 - attended the visit
 - missed the visit
- For off-treatment (i.e., discontinued treatment prior to visit) those who:
 - attended the visit
 - missed the visit
- Who withdrew from the study prior to the visit

If a subject does not have a record for a visit and did not withdraw from the study, then the record will be counted as due to missing. For subjects who withdraw from the study then the date of study withdrawal will be used to assess whether the subject missed the visit. Any missing records prior to this date will be classed as missing and any missing records after this date will be classed as a withdrawal.

9.2. DEMOGRAPHIC AND BASELINE CHARACTERISTICS

Demography (sex, race, ethnicity, age at consent [years], weight, height, body mass index (BMI) at screening and menopausal status) will be summarized. Age, weight, height and BMI will be summarized using summary statistics for continuous variables. Sex, categorical age (18 – 25 years, 26 - 45 years and 46 – 64 years and ≥ 65 years), race, ethnicity and menopausal status (men, pre-menopausal women and post-menopausal women) will be summarized as categorical variables.

All subgroups defined in [Section 8.5](#) will be summarized as categorical variables. In addition, screening 12MWD will be summarized categorically (≤ 500 m or > 500 m and ≤ 650 m or > 650 m). In the event of a mis-stratification, the 12MWD screening categorical split will be based on the actual screening data.

The following baseline endpoints will also be summarized as continuous variables:

- 12MWD – screening and baseline distance
- PROMIS T-score
- MFIS scale – physical, cognitive, psychosocial and total score
- 30 second sit to stand count
- PGI-S – muscle and fatigue (note, summarized as categorical variables only)

The duration of PMM symptoms (years) will be summarized using summary statistics for continuous variables.

Duration of PMM symptoms (years) = Age at consent – Age at onset of PMM symptoms

These data will be summarised for the safety, FAS, PP and CScAS sets. Menopausal status will only be summarized for the CScAS. If the SAF and FAS are the same only the one will be presented (as Safety/FAS).

9.3. MEDICAL HISTORY AND CONCOMITANT DISEASES

Medical history will be coded using Medical Dictionary for Regulatory Activities (MedDRA) version 23.1.

A separate summary of past and current medical history will be presented for the safety set by System Organ Class (SOC) and Preferred Term (PT) with counts and percentages. Each subject will be counted only once in each SOC or SOC/PT summary. In the summary tables, medical history will be presented by decreasing frequency of subjects overall within each SOC and then similarly by decreasing frequency of subjects overall within each PT. In cases of SOCs or PTs with equal frequencies, medical history will be sorted alphabetically.

Past medical history events are defined as events reported with an end date prior to Day 1 and current medical history events are ongoing events on Day 1. If a partial end date is recorded, the following convention will be used to assign the event:

- If a partial end date is missing a day and the month/year is the same, or after, the start date of dosing then the event will be assumed to be current; otherwise, it will be assumed to be a past event
- If a partial end date is missing a month and only the year is present and the year is \leq the year that study dosing starts, then it will be assumed to be a past event. Medical history is collected at the screening visit and therefore events ending on or after the screening visit should be recorded with at least a month and year for the end date
- If the end date is missing, then it will be assumed to be a current event.

The following PTs, which are associated with the disease under study, will be listed but excluded from the summaries:

- mitochondrial myopathy
- progressive external ophthalmoplegia
- MELAS syndrome,
- myoclonic epilepsy and ragged-red fibres,
- Kearns-Sayre syndrome,
- gene mutation,
- mitochondrial DNA deletion
- mitochondrial encephalomyopathy

9.4. PRIOR AND CONCOMITANT MEDICATIONS

Prior and concomitant medications will be coded using World Health Organization (WHO) Drug Dictionary version WHODRUG GLOBAL B3 September 1, 2020.

Prior medications will be defined as those medications started prior to the administration of study drug on Day 1. Concomitant medications will be defined as those medications taken following administration of study drug on Day 1. Hence medications started before receiving the study dose but continuing after will be considered as both prior and concomitant medications. Concomitant medication summaries will be repeated for those medications that are taken whilst on-treatment (ignoring dosing interruptions) or started within 7 days after the last dose of study drug.

Medication will be summarised for the safety and the DXA CScAS by anatomic therapeutic chemical (ATC) level 2 (therapeutic main group) and ATC level 5 (PT medication name) with counts and percentages. Prior and concomitant medications will be presented by descending frequency in ATC and PT within ATCs over all subjects. A subject who takes more than one medication will be counted only once if these medications belong to the same extended ATC classification. These summaries will be repeated for medications that have an adverse impact or positive impact on the bones; a medical review of unique medications will be performed prior to database lock to identify these medications.

All data will be listed for the safety set and a variable will be included to identify whether the medication is prior, concomitant or both prior and concomitant. The listing will also identify whether the start date of medication was after the date of last dose of study drug plus 7 days for those subjects who have discontinued treatment.

If either the start or stop date of medication is missing, the most conservative case will be considered when assigning medications to categories. So, for a missing start date where stop date is after start date of dosing or missing, the date will be imputed as the dosing start date. For a missing start date where stop date is on or before the start date of dosing, the date will be imputed as the day before the stop date and the event will be classified as a prior medication; for a missing stop date the date will be imputed as the last study date. If a partial date is recorded, the following convention will be used to assign the medication:

- If a partial date is missing a start day and the month/year is the same as the start date of dosing then use the dose start date if the stop date is after the dose start date or the stop date is missing, else '01' will be used for the day; if a start date is missing a month and the year is the same as the start date of dosing then use the dose start date if the stop date is after the dose start date or the stop date is missing, else January will be used for the start month.
- If a partial date is missing a stop day and month/year is same as last study date then use last study date, else last day of the given month will be used for the stop day; if a stop date is missing a month and the year is the same as last study date then use last study date, else December will be used for the stop month.

Concomitant non-drug therapies will also be listed for the safety analysis set.

9.5. TREATMENT EXPOSURE

Duration of treatment, days on treatment, number of capsules taken, and treatment compliance, will be summarized for the FAS using descriptive statistics. Duration of treatment will also be summarized using 4-week categories (e.g., ≤ 4 weeks, >4 to ≤ 8 weeks, ..., >16 to ≤ 20 weeks, >20 weeks); and treatment compliance will also be summarized using the categories $<80\%$, $80-120\%$ and $>120\%$.

- Duration of treatment in days is defined as (date of last dose minus date of first dose plus 1 day). Values will be presented to 1 decimal place.
- Days on treatment is defined as the duration of treatment minus the number of days the subject is instructed to not take their medication (e.g., dose interruption due to AE)
- Number of capsules expected to be taken is defined as the days on treatment multiplied by the number of capsules to be taken each day (2 per day)
- Number of capsules taken is defined as number of capsules dispensed minus number of capsules returned
- Treatment compliance (%) is defined as $100 * \text{number of capsules taken} / (\text{number of capsules expected to be taken})$. Values will be presented to 1 decimal place.

If study drug is not returned, the listing will present a compliance range; the lower limit will assume no study drug taken for the containers not returned and, the upper limit will assume all study drug taken for the containers not returned. The compliance listing will also include number of capsules dispensed and number of capsules returned.

If study drug is not returned the summary will consider number of capsules taken as missing. However, for the treatment compliance categorical summary, the subject may be counted if their range falls entirely within one treatment compliance category (e.g., if the range is 40-60% they will be counted in the count for the <80% category).

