3.5 Termination or Suspension of Investigational Sites

A study site may be terminated prematurely or suspended if the site (including the Investigator) is found to be in significant violation of GCP, the protocol, or the contractual agreement, or is unable to ensure adequate performance of the study, or for reasons as otherwise permitted by the contractual agreement.

3.6 Conditions for Individual Subject Discontinuation of Study Drug or Withdrawal from the Study

[figure not shown]
The primary reason for permanent discontinuation of a subject from the study drug should be recorded in the electronic Case Report Form (eCRF). Individual subjects may be discontinued from the study drug in the following circumstances:

1. Concurrent enrolment in other clinical studies involving investigational products or enrolment in other types of clinical research judged not to be scientifically or medically compatible with this study.
2. Use of a prohibited concomitant medication.
3. Major protocol deviation e.g., the discovery after administration of the first dose of study medication that the subject failed to meet protocol entry criteria or did not adhere to protocol requirements, and continued participation poses an unacceptable risk to the subject’s health or undermines the ability to achieve the objectives of the study.

4. Lost to follow-up. The subject did not return to the study center and attempts to contact the subject were unsuccessful. Attempts to contact the subject must be documented.
5. Evidence of pregnancy during the treatment period of the study.
6. Clinically significant changes from baseline in ECG recordings considered treatment-related including an increase from baseline in heart rate corrected QT interval using Fridericia's formula (QTcF) to a value of ≥ 500 millisecond (msec). Single ECGs should be repeated at 5-minute intervals, 3 times, to confirm any increased QTcF interval values. In the event of an increased QTcF interval of ≥ 500 msec, the subject must be monitored until the value returns to below 500 msec.
7. Clinically significant muscle injury including test abnormalities (e.g., CK) as defined in [Section 3.7.1](#).
8. Clinically significant liver toxicity including test abnormalities (e.g., ALT/AST) as defined in [Section 3.7.2](#).
9. Clinically significant kidney toxicity including test abnormalities (e.g., creatinine levels) as defined in [Section 3.7.3](#).

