7.3. SAFETY ANALYSIS SET

The safety set will include all subjects who signed the informed consent form, completed screening and received at least one dose of study drug. The safety analysis set summaries will be based on the actual treatment received. The safety analysis set will be used for all baseline and safety analyses.

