7.4. FULL ANALYSIS SET

The full analysis set (FAS) will include all subjects in the randomized set who received at least one dose of study drug and have not been subsequently discontinued from the study for failing eligibility criteria. Subjects will be analysed according to the treatment they were assigned at randomization. The FAS will be used for baseline analyses and will be the primary analysis set for efficacy.

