12. ANALYSIS OF SAFETY DATA

All safety evaluations will be performed using the safety analysis set unless specified otherwise.

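### SAP 9.5 summarises exposure only for the FAS by assigned arm, while safety data are summarised for the Safety Set by treatment received, so the two can describe different subjects and arms

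*SAP*

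**What the plan says.** SAP 9.5 (Treatment Exposure) names one analysis set: "Duration of treatment, days on treatment, number of capsules taken, and treatment compliance, will be summarized for the FAS using descriptive statistics". Neither document plans an exposure summary for the Safety Set.

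SAP 7.4 limits the FAS to randomized subjects who "received at least one dose of study drug and have not been subsequently discontinued from the study for failing eligibility criteria". On grouping it says: "Subjects will be analysed according to the treatment they were assigned at randomization".

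SAP 7.3 defines the Safety Set by receipt of at least one dose, with no exclusion for later-discovered ineligibility. On grouping: "The safety analysis set summaries will be based on the actual treatment received". On use: "The safety analysis set will be used for all baseline and safety analyses". SAP 12 repeats this for the safety chapter: "All safety evaluations will be performed using the safety analysis set unless specified otherwise".

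**The concern.** An exposure table tells the reader of the safety tables how long the subjects in them were treated, and with what. For that it should cover the same subjects in the same arms. Here the two can separate in two ways: in membership, through the eligibility exclusion in the FAS, and in arm, through assigned versus received treatment.

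The link to exposure is practical, because several safety summaries depend on the date of last dose:

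- SAP 8.2 defines an on-treatment safety measurement as one taken up to one day after last dose.
- SAP 12.1 repeats some adverse event tables for events emerging no more than 7 days after last dose.
- SAP 12.2 (laboratory values of potential clinical importance) and SAP 12.5 (maximum QTcF) use on-treatment values only.

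A reader of those tables would want duration of treatment for the same population and grouping.

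**Working it through.** The plan gives no figure on this point to reproduce. The check is a comparison of definitions, followed by an illustration of size on stated assumptions.

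**1. The two sets side by side**

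| | Exposure (SAP 9.5) | Safety data (SAP 12) |
|---|---|---|
| Set | FAS | Safety Set |
| Dosed, later discontinued from study as ineligible | Out | In |
| Arm | As assigned | As received |

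**2. Can the sets differ in membership?** Yes. Protocol 3.6 lists as a ground for stopping study drug "the discovery after administration of the first dose of study medication that the subject failed to meet protocol entry criteria". If such a subject is discontinued from the study for that reason, SAP 7.4 removes them from the FAS and SAP 7.3 keeps them in the Safety Set. The protocol's own FAS (Protocol 8.1.3) has no such exclusion, so this gap comes from the SAP. The SAP's change history shows that the exclusion was added deliberately in version 2.0.

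**3. Can they differ in arm?** Yes. SAP 7.6 lists receipt of the wrong medication as a reason for exclusion from the per protocol set only. Such a subject stays in the FAS under the assigned arm and appears in the Safety Set under the treatment received.

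**4. Does the SAP deal with this elsewhere?** For baseline tables, yes: SAP 9.2 summarises both sets and shows one table only if they are the same. SAP 9.4, immediately before 9.5, summarises medications on the Safety Set. SAP 9.5 has neither provision.

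**5. Illustration of size.** The documents give no counts of omitted or mis-dosed subjects. The counts and omitted-subject durations below are assumptions, with about 200 dosed subjects, about 100 per arm, and 24 weeks (168 days) of planned treatment.

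*Share of dosed subjects absent from the exposure summary*, k / 200:

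- k = 0: 0%
- k = 1: 0.5%
- k = 2: 1%
- k = 5: 2.5%
- k = 10: 5%

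*Gap in mean duration within an arm*, (k / 100) × (FAS mean − mean of omitted subjects), taking the FAS mean as 24 weeks:

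- k = 0: 0 weeks.
- k = 1, omitted subject treated for 4 weeks: (1 / 100) × 20 = 0.2 week.
- k = 5, each treated for 4 weeks: (5 / 100) × 20 = 1.0 week. Directly, the Safety Set mean is (95 × 24 + 5 × 4) / 100 = 23.0 weeks against 24.0 for the FAS.
- k = 5, each treated for 20 weeks because ineligibility was found late: (5 / 100) × 4 = 0.2 week.

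*Treatment days summarised in the opposite arm from the adverse events*: each subject given the wrong treatment throughout contributes up to 168 days, against 100 × 168 = 16,800 planned days in an arm, or 168 / 16,800 = 1%.

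**The case against.** The best defence is that naming the FAS is an explicit choice and contradicts no other section. Exposure sits in SAP Section 9, not in the safety chapter, so the rule in SAP 12 does not clearly govern it. Protocol 8.4 asks for compliance by treatment group without naming a set, and Protocol 8.6 requires no exposure summary. SAP 8.2 lists all data for every randomized, dosed subject, SAP 9.5 adds a compliance listing with capsules dispensed and returned, and SAP 9.1 reports the number in each analysis set. Any gap would be visible and could be followed up subject by subject. All of this stands. It makes the point an improvement and not the correction of an error. Listings still do not give the reader a summary by arm for the population on which safety is judged.

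Three stronger readings are tempting, and the documents do not support them:

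- *That adverse event rates are distorted because exposure is their denominator.* SAP 12.1 plans numbers and percentages of subjects, with no person-time or exposure-adjusted rate.
- *That the omitted subjects must have short exposure, so duration is necessarily overstated.* SAP 7.4 sets no time limit, and Protocol 3.6 says only that discovery follows the first dose. Shortened exposure is plausible but not part of the definition.
- *That such subjects exist.* Protocol 3.6 and SAP 7.6 provide for ineligibility found after dosing and for wrong medication. They are not evidence that either occurred.

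A remedy that moved duration and capsules to the Safety Set but left compliance on the FAS would also be open to criticism. SAP 9.5 computes compliance from days on treatment and capsules taken, so the ratio and its components would then rest on different subjects and possibly different arms.

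**Conclusion.** The mismatch holds as a conditional statement. Any dosed subject discontinued from the study for failing eligibility would be missing from the exposure summary while remaining in the safety tables and the listings. Any subject who received the other treatment would have exposure summarised in the opposite arm from their adverse events. Adverse event percentages, efficacy results and type I error do not change.

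The size cannot be fixed from the documents. It is zero if sets and groupings coincide. Under the assumed range of 0 to 5 omitted subjects per 100 in an arm, with the shortest exposure considered, mean duration differs by 0 to 1.0 week. Each subject mis-dosed throughout accounts for up to about 1% of an arm's planned treatment days. The point is a free improvement.

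**What to change.** In SAP 9.5, summarise duration of treatment, days on treatment, capsules taken and compliance together for the Safety Set by treatment actually received. Keep the FAS summary by assigned arm as an addition. If the two sets and the two groupings are identical, present one combined table, following the rule for baseline tables in SAP 9.2.

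The cost is a change to one sentence and at most one extra table. It needs no new data, and the subject-level derivations stay as they are.
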